---

### Funder

This study is funded by the Imperial Biomedical Research Centre.

This protocol describes the study and provides information about procedures for entering participants. Every care was taken in its drafting, but corrections or amendments may be necessary. These will be circulated to investigators in the study. Problems relating to this study should be referred, in the first instance, to the Chief Investigator.

This study will adhere to the principles outlined in the **UK Policy Frame Work for Health and Social Care Research**. It will be conducted in compliance with the protocol, the Data Protection Act and other regulatory requirements as appropriate.

**GLOSSARY OF ABBREVIATION**

AUC	Area under the curve
ARVC	Arrhythmogenic right ventricular cardiomyopathy
DCM	Dilated cardiomyopathy
ECG	Electrocardiogram
Echo	Echocardiogram
HCM	Hypertrophic cardiomyopathy
ICC	Inherited cardiac conditions
LQTS	Long QT syndrome
NN	Neural network
RASE	Rare Arrhythmia Syndrome Evaluation
RBBB	Right bundle branch block
UHF-ECG	Ultra-high frequency electrocardiography
VT	Ventricular tachycardia
VF	Ventricular fibrillation

## STUDY SUMMARY

TITLE	Unmasking Concealed Arrhythmia Syndromes
DESIGN	Proof-of-concept studies to develop ECG AI algorithms, followed by case-control diagnostic accuracy study and prospective cohort studies
AIMS	
 
1. To develop machine learning algorithms for 12-lead ECGs to detect diagnostic features of Brugada syndrome.
 
2. To test and validate these algorithms prospectively in participants wearing ambulatory ECG recording devices.
 
3. To ascertain the role of UHF-ECG for risk stratification in patients with inherited arrhythmogenic conditions
 

OUTCOME MEASURES	
 
• Brugada ECG algorithm sensitivity, specificity and AUC value for both 12 lead ECGs and 12 lead vest ECGs
 
• Yield of extended duration multi-electrode ambulatory ECG monitoring to detect the Brugada ECG pattern in concealed Brugada syndrome
 
• The utility of extended duration multi-electrode ambulatory ECG monitoring to detect a single case of underlying Brugada or LQTS manifestation in idiopathic VF
 

POPULATION	Healthy volunteer controls, patients with a diagnosis of Brugada syndrome, patients with a diagnosis of idiopathic VF syndrome and patients with other inherited arrhythmogenic conditions
ELIGIBILITY	
Participant sets (Appendix 1):
 
 
• Group A – healthy volunteers
 
• Group B – concealed arrhythmia syndrome patients (patients with a normal ECG with a known underlying arrhythmic diagnosis)
 
• Group C – manifest arrhythmia syndrome patients (patients with an arrhythmic syndrome with an abnormal ECG)
 

DURATION	November 2023 – November 2026 (3 years)

## 1. INTRODUCTION

### 1.1 BACKGROUND

Sudden cardiac arrest is often the first clinical presentation of an inherited arrhythmia syndrome (1). In up to 37% of young sudden cardiac arrest survivors, no clear cause is identified despite comprehensive clinical evaluation (2). These patients and their relatives, who are likely to harbour a genetic predisposition for life-threatening arrhythmias, can remain undiagnosed for years as phenotypic changes may not be apparent at the time of their assessment. Patients with these concealed arrhythmia syndromes can also present with syncope or palpitations with apparently normal cardiac investigations at the time of presentation. If a diagnosis cannot be made, they cannot be protected from their potential risk of sudden arrhythmic death.

Concealed arrhythmia syndromes may manifest themselves transiently during day-to-day physiological provocations such as peaks, troughs and sudden changes in cardiac autonomic tone. For example, long QT syndrome can manifest immediately after exercise, while Brugada ECG patterns can emerge during fever and deep sleep (3). It is not currently practicable to conduct sufficiently prolonged and detailed ECG assessment to sensitively detect these transient electrical manifestations. Instead, we are currently obliged to conduct short term provocation tests, using exercise, orthostasis, and drugs, which have low diagnostic yield and (in the case of ajmaline) can induce fatal arrhythmias (4). Invasive electrophysiology studies and genetic testing can identify some rare cases but are most often non-contributory (5–7).

We postulate that novel non-invasive ECG-based diagnostic techniques and long term ambulatory monitoring may further augment our ability to detect these concealed arrhythmia syndromes.

## 2. STUDY OBJECTIVES

Primary objective: To combine novel non-invasive ECG techniques and long term ambulatory ECG monitoring to unmask concealed arrhythmia syndromes

Secondary objective: To explore the utility of non-invasive ECG techniques for arrhythmic risk stratification

## 3. STUDY DESIGN

### 3.1 RECRUITMENT

#### Brugada ECG AI training

We will collate anonymised Brugada ECG data from UK and international centres. We will collaborate with site-specific representatives to coordinate secure ECG data transmission and acquisition. All ECG data will be anonymised at the point of collection. Consent will not be sought as only anonymised ECGs will be obtained. There will be no access to patient-identifiable data from the research team and all data will be fully anonymised prior to transfer. These ECGs will be acquired from pre-existing hospital digital infrastructure, namely the electronic health record or ECG data management system. Data will be transmitted securely through trusted secure data transfer systems where available. Where this option is not available, ECG data will be physically retrieved via a researcher visiting the centre and copying anonymised data onto an encrypted hard drive.

We will acquire digital ECG recordings as well as scanned paper ECGs of patients with established Brugada syndrome. Paper ECGs will be scanned and imported onto local secure storage. We will also gather anonymised ECG data from Imperial College Healthcare NHS Trust patients. We aim to acquire around 3000 patient ECGs in total for AI training. Where available, corresponding clinical data will also be collected alongside participants' ECGs, including results of any relevant genetic testing and other investigations including ajmaline provocation testing.

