## **3.3 METHODOLOGY**

### **Study A: Brugada ECG AI development**

The research team will collate at least 3000 ECGs, representing the 3 different categories previously mentioned. All ECGs will be either digital or converted to a digital format using in-house developed software. ECGs will subsequently be processed to enable direct extraction of the ECG complexes from the recordings. The resulting ECG data will be segmented to enable labelling by experts in Brugada ECG analysis.

The anonymous ECG data will be reviewed and annotated by experts. Each ECG will be labelled by 5 individual experts from a larger pool of experts, who will collectively share the task of ECG labelling for our entire training set. Experts will be comprised from the ICC specialists at Imperial College Healthcare NHS Trust, as well as our research collaborators within the UK and internationally. The categorisation of each case will be determined by expert majority agreement.

The labelled ECG data will be divided into the training set (75% of ECG data) and a separate hold-out validation set (25% of ECG data). The training set will be used to train separate neural networks (Appendix 2). Once the neural networks have been developed, they will be tested for their accuracy against a hold-out validation dataset.

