### Study A

ECG data will be obtained from the host institution (Imperial College Healthcare NHS Trust) as well as external centres both in the UK and internationally. This data will derive from patients identified by the site-specific representatives, who will coordinate secure ECG data transmission and acquisition. All ECG data will be collected anonymously or anonymised at the point of collection. Consent will not be sought as only anonymised ECGs will be obtained. There will be no access to patient-identifiable data from the research team and all data will be fully anonymised prior to transfer.

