## **7. STATISTICS AND DATA ANALYSIS**

We expect to have access to over 3000 patients' worth of ECG data to train and validate our neural networks, comprising a similar proportion of Brugada and non-Brugada ECGs. Our group has published extensively regarding applications of AI to ECG data (13–17) and includes experienced, independently-funded clinician scientists and engineers with expertise in machine learning. They will guide me in developing neural networks for ECG classification tasks and signal processing. As we will be employing a very similar methodology to our previous successful ECG AI projects in this experiment, we are confident that this quantity of ECG data will be sufficient to develop highly accurate neural networks.

The accuracy of the prolonged duration ambulatory ECG recordings will be calculated using a binomial distribution. Assuming an actual accuracy of 95% and a target accuracy of >85% for ECG analysis discriminating between healthy normal participants and manifest Brugada patients, 90 patients will provide greater than 80% power in demonstrating that the measured accuracy is significantly greater than 85% at the two-tailed 5% significance level. To achieve 90 patients with some loss to follow up, I will recruit 50 healthy volunteers and 50 manifest Brugada patients.

McNemar's test will be used for paired analysis of 24-hour 12 lead Holter and prolonged ambulatory ECG recordings in the concealed arrhythmia patient set. Historical data report 20 to 34% sensitivity for 24-hour Holter for detection of the Brugada ECG pattern in patients with concealed Brugada syndrome (5,6). Assuming 25% sensitivity for 24-hour Holter and 60% for prolonged ambulatory ECG recordings beyond 24 hours, with the prolonged ambulatory ECG recordings being able to identify 80% of 24-hour Holter-identified cases, 35 patients would be needed to provide 90% power at the 5% significance level. I will recruit 50 patients.

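### Scanned paper ECGs are specified only for Brugada patients and the non-Brugada ECGs have no stated source or format, so the pooled hold-out could overstate the 12-lead accuracy of NN1 and NN3

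*Protocol*

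**What the plan says.** - **Section 3.1, Brugada ECG AI training.** The collection opens with "We will collate anonymised Brugada ECG data from UK and international centres" and continues "We will acquire digital ECG recordings as well as scanned paper ECGs of patients with established Brugada syndrome". For the host Trust it adds "We will also gather anonymised ECG data from Imperial College Healthcare NHS Trust patients", without giving the disease status of those patients.
- **Section 4.5, Consent, Study A.** ECG data come from the host institution "as well as external centres both in the UK and internationally". This is not limited to Brugada patients, and paper is not mentioned.
- **Section 3.3, Study A.** On format: "All ECGs will be either digital or converted to a digital format using in-house developed software". Five experts label each ECG and the majority decides the category. Then: "The labelled ECG data will be divided into the training set (75% of ECG data) and a separate hold-out validation set (25% of ECG data". Neither format nor centre enters the description of the split, and this hold-out is the only accuracy test described within Study A.
- **Section 7.** The data set is expected to cover more than 3000 patients, "comprising a similar proportion of Brugada and non-Brugada ECGs".
- **Section 3.4 and Appendix 2.** Sensitivity, specificity and AUC on 12-lead ECGs are primary outcomes. NN1 contrasts phenotype-positive Brugada with non-Brugada ECGs, and NN3 contrasts phenotype-negative Brugada with non-Brugada ECGs. NN2 is trained on expert beta-angle measurements from all three groups. NN4 contrasts SCN5a status among genetically tested patients.

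No section states which centres supply the non-Brugada ECGs or in what format.

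**The concern.** A neural network uses whatever separates the two classes in its training data. If scanned tracings occur mostly among the Brugada ECGs, traces of scanning and conversion help to predict the label. The same holds for the acquisition signature of a centre that sends mainly one class. A hold-out drawn from the same pool contains the same association, so a network that partly recognises source is rewarded in testing as it was in training.

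At stake are the primary 12-lead results for NN1 and NN3, the two networks trained directly on Brugada versus non-Brugada. NN3 is the more exposed. Its cases show no Brugada pattern and are identified by clinical diagnosis, so a reader has no visible feature against which to judge what the network learned.

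Which controls are requested, and in what form, is settled when the data are acquired. Later analysis cannot supply same-format controls that were never collected.

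**Working it through.** The protocol gives no figure for this risk, so there is none to reproduce. The check is how much a rule that sees only the source could score, and what changes that score.

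**Inputs from the protocol.** Total about 3000 ECGs. Training 0.75 × 3000 = 2250; hold-out 0.25 × 3000 = 750. With similar class proportions, about 1500 ECGs are non-Brugada, and about 375 of each class fall in the hold-out. NN1 and NN3 each use only part of the Brugada ECGs, so their own hold-outs would be smaller. The AUC below does not depend on class mix.

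**Assumed inputs, not in the protocol.** f is the share of Brugada ECGs carrying a source flag (for example, scanned paper), and g is the share of non-Brugada ECGs carrying it. The flag is taken to remain fully recognisable after conversion to digital form.

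**Formula.** A rule that calls an ECG Brugada when the flag is present has sensitivity f and specificity 1 − g. For a yes/no marker, AUC = (sensitivity + specificity)/2 = (f + 1 − g)/2. With g = 0 and f = x this is 0.5 + x/2.

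| f | g = 0 | g = 0.1 | g = f |
|---|---|---|---|
| 0.1 | 0.55 | 0.50 | 0.50 |
| 0.3 | 0.65 | 0.60 | 0.50 |
| 0.5 | 0.75 | 0.70 | 0.50 |
| 0.8 | 0.90 | 0.85 | 0.50 |

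The score depends on the difference f − g, that is, on how unevenly the classes are sourced.

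**Does stratifying the split help?** A 750-ECG hold-out was simulated 1000 times at f = 0.5, g = 0. A simple random split gave a mean source-only AUC of 0.75 (central 95% of runs 0.723 to 0.776). A split stratified by class and source also gave 0.75 (0.737 to 0.763). Stratifying narrows the spread and leaves the bias where it was, because it preserves the association in both parts.

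**What does help.** Within a stratum of one format and one centre, the flag is constant, so a source-only rule scores 0.50. Accuracy therefore has to be computed within strata that contain both classes and then combined, or the classes have to be matched on source. Pooling mixed strata with unequal shares is not enough: f = 0.5, g = 0.1 still gives 0.70.

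**Price of a digital-only figure.** If g = 0, the digital part of the hold-out is 375 + 375(1 − f): 637.5 at f = 0.3, 562.5 at f = 0.5 and 450 at f = 0.8, against 750.

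**The case against.** - **External sourcing is not confined to Brugada.** From section 3.1 alone, a reader might infer that outside centres supply only Brugada ECGs and that centre and class are therefore confounded. The documents do not support that: the Study A consent text describes external sourcing for ECG data in general. This stands, and it makes centre confounding a possibility only. That text does not say that outside centres send non-Brugada ECGs, however, and it leaves the paper statement in section 3.1 uncontradicted.
- **Silence is not exclusion.** Section 3.1 does not say that non-Brugada ECGs are digital only. This stands too, and it is why the AUC values above are illustrations.
- **All ECGs end up digital.** Section 3.3 converts every non-digital ECG and then extracts complexes. This may weaken the cue. But conversion is applied only to the non-digital ECGs, so it can leave a signature of its own, and the protocol does not claim otherwise.
- **Experts fix the labels.** They do, but that does not determine which features a network uses to predict the label.
- **Study B is a separate test.** A reader might infer that source recognition could never come to light. That goes too far: Study B applies the algorithms to prospective ambulatory recordings in healthy volunteers and manifest Brugada patients, with a powered comparison (95% assumed accuracy against an 85% target). It is only a partial check. It cannot correct the 12-lead figures, a poor result could not be told apart from a device effect, and its sensitivity is measured in manifest disease, which is not NN3's target.
- **The split belongs in an analysis plan.** Details of the split may well be given in one that is not shown. The choice and format of controls are data-acquisition matters, which section 3.1 addresses.
- **Not every network is affected alike.** A reader might extend the point to all four. NN2 and NN4 are not trained on the Brugada versus non-Brugada contrast, so the argument does not carry over to them directly.

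**Conclusion.** The point holds as a risk that the protocol leaves open. Scanned paper is described only for established Brugada syndrome, the source and format of about half the data are unstated, and the hold-out shares the pool with the training data. Any link between class and format or centre would therefore carry into the primary 12-lead sensitivity, specificity and AUC of NN1 and NN3.

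The protocol does not show that such a link exists, and no stated figure is shown to be wrong. The size is conditional. With no flagged non-Brugada ECGs and a fully recognisable flag, source alone would score an AUC of 0.55 to 0.90 as the flagged share of Brugada ECGs runs from 10% to 80%. With equal shares it scores 0.50. Partial recognisability after conversion, or some paper among the controls, would lower the upper values. The matter should be settled while ECGs are still being requested.

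**What to change.** 1. State the source and format of the non-Brugada ECGs, and align section 3.1 with the Study A consent text in section 4.5.
2. Request non-Brugada ECGs from the same centres and in the same formats as the Brugada ECGs.
3. Base the headline hold-out accuracy of NN1 and NN3 on format and centre strata that contain both classes, computed within strata and then combined. Alternatively, hold out whole centres that supply both classes in the same formats.
4. Report digital-only accuracy beside the overall figure.

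Stratifying the 75/25 split should not be offered as the remedy by itself.

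The cost is wording in the data requests and some analysis time. The downside is a somewhat smaller headline hold-out set, with wider intervals, and possibly lower reported accuracy.

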### **Prospective studies**

200 patients will be recruited in total. The direct care team will screen the records and identify patients followed up at Imperial College Healthcare Trust that are suitable for the study. Patients will also be identified at several national ICC centres, via our collaborators, and invited to attend the Imperial College London Pert Rose Research Unit for recruitment into our study.

We will recruit 3 groups of participants:

- Group A – healthy volunteers
- Group B – patients with a normal ECG and an underlying inherited arrhythmic syndrome
- Group C – patients with an arrhythmic syndrome with an abnormal ECG

We will be aiming for an approximately even distribution of participants to be recruited to each group.

The direct care team will obtain consent to share their information with the research care team. Once the patient has consented to their information being shared, a member of the research team will contact the patient and explain the details of the research study. Written consent will be gained prior to any tests taking place.

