### Study B: Remote arrhythmia diagnostics

In this study, we will undertake validation studies to assess the robustness, accuracy and applicability of the aforementioned AI algorithms (i.e. neural networks) on ECG recordings from several different ambulatory monitoring modalities. This protocol will encompass participants recruited in Groups A-C.

Commented [KS1]: Added for clarity

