## 6. ASSESSMENT & FOLLOW UP

Patients will be followed up over a 3 month period remotely while wearing their ambulatory ECG. 12-lead ECG and UHF-ECG data will be collected at the index visit. Symptom diaries and ambulatory ECG recordings will be collected at the end of the study interval. Any incidental findings that we identify during the study will be reviewed by the research team and reported to the GP and also the cardiology team normally looking after the patient. We will continue to follow up all patients after their last contact with the research team through review of the electronic health record and any clinical cardiac device checks up until the end of the study on 1st April 2027, at which time all follow up will cease. The prospective studies

will end after 200 patients have undergone the 3 month interval of follow up or by the study end date of 1st April 2027.

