We are also seeking to identify at least one extra patient with Long QT or Brugada syndrome by performing extended duration monitoring beyond standard 12 lead 24-hour Holter. Registry data (7–9) suggests that between 3–4% of idiopathic VF patients eventually receive a specific diagnosis of Brugada syndrome through conventional diagnostic testing and routine clinical follow up. A similar proportion are diagnosed with long QT syndrome. If extended duration monitoring can identify half of these (4%), then 50 patients will provide 87% power to detect at least one extra case (simulated through repeat sampling of a binomial distribution).

We also plan to recruit 100 patients with other inherited arrhythmic conditions, who can be subdivided into high and low arrhythmic risk groups. We believe that these cohort sizes will be adequate to gather sufficient pilot data to enable identification of subtle changes in UHF-ECG profiles.

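### The section 7 cohorts add to 300, but sections 3.1 and 6 recruit and end at 200, split about evenly over Groups A-C

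*Protocol*

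**What the plan says.** All references are to the protocol.

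- **Section 3.1, Prospective studies.** "200 patients will be recruited in total". The three groups then listed include healthy volunteers as Group A. On allocation: "We will be aiming for an approximately even distribution of participants to be recruited to each group".
- **Section 6.** The prospective studies "will end after 200 patients have undergone the 3 month interval of follow up", or by 1 April 2027.
- **Section 7, accuracy in healthy volunteers versus manifest Brugada.** "I will recruit 50 healthy volunteers and 50 manifest Brugada patients", to secure 90 after losses.
- **Section 7, concealed Brugada (McNemar comparison).** "35 patients would be needed to provide 90% power at the 5% significance level. I will recruit 50 patients".
- **Section 7, idiopathic VF.** At a 4% detection rate, "then 50 patients will provide 87% power to detect at least one extra case".
- **Section 7, last paragraph.** "We also plan to recruit 100 patients with other inherited arrhythmic conditions", to be divided into high and low arrhythmic risk for the UHF-ECG work.
- **Section 3.3.** Of Study B: "This protocol will encompass participants recruited in Groups A-C". Study C is given the same three groups, so neither study has a recruitment pool of its own.
- **Appendix 1.** Concealed Brugada and idiopathic VF are separate entries, both in Group B. Manifest Brugada is in Group C.

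**The concern.** The recruitment total and end rule in sections 3.1 and 6 cannot be met together with the cohorts in section 7. A team that recruits to section 7 passes 200 before it finishes. A team that stops at 200 with the four powered cohorts full has enrolled none of the 100 other patients, whom section 7 names as the group to be divided by arrhythmic risk. UHF-ECG risk stratification is the third aim in the Study Summary and a secondary outcome in section 3.4.

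The even split is a second, separate conflict. If it is followed, Group B is too small for both of its powered cohorts. Both support primary outcomes in section 3.4: the yield of extended monitoring in concealed Brugada and in idiopathic VF.

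**Working it through.** **1. The plan's component figures reproduce.**

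- *Accuracy* (true 95% against 85%, two-tailed 5%, n = 90). Exact binomial with 2.5% in the upper tail: reject at 84 or more correct. P(X ≥ 84 | 0.85) = 0.013; P(X ≥ 84 | 0.95) = 83.6%. The plan says over 80%.
- *Concealed Brugada* (25% against 60%, with 80% of Holter-positive cases also found). Found by both: 0.8 × 0.25 = 0.20. Discordant cells: 0.60 − 0.20 = 0.40 and 0.25 − 0.20 = 0.05. Their sum is 0.45 and their difference 0.35. With two-sided 5% (sidedness is not stated here) and 90% power, n = [1.960√0.45 + 1.282√(0.45 − 0.35²)]² / 0.35² = 34.2, so 35. Power at 35 is 90.7% asymptotic or 89.2% exact. The plan says 90%.
- *Idiopathic VF* (4%, n = 50). 1 − 0.96^50 = 87.0%. The plan says 87%.

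**2. The total does not reproduce.**

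| Cohort in section 7 | Group | Planned | Smallest stated size |
|---|---|---|---|
| Healthy volunteers | A | 50 | 90 together with manifest Brugada |
| Manifest Brugada | C | 50 | (included above) |
| Concealed Brugada | B | 50 | 35 |
| Idiopathic VF | B | 50 | 50 |
| **Powered cohorts** | | **200** | **175** |
| Other inherited conditions | B or C | 100 | – |
| **All cohorts** | | **300** | **275** |

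Places left for the 100 within a total of 200: 200 − 200 = 0 as planned, and 200 − 175 = 25 with every allowance for loss removed.

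**3. Readings that might rescue 200.**

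- The total excludes volunteers: 300 − 50 = 250. Section 3.1 also lists volunteers among the groups recruited.
- Concealed Brugada and idiopathic VF are the same people: 250. Appendix 1 lists them separately, and the McNemar rates are for concealed Brugada.
- The 100 already include the 50 idiopathic VF patients: 250. Section 7 presents the 100 as an addition and as having different conditions.
- Excluding volunteers and also assuming one of these overlaps gives 200. The protocol states neither, and Group A would be 50 of 250 participants, against an even share of 83.

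**4. The even split.** 200 / 3 = 66.7 per group. The powered cohorts fall 50/100/50 over A/B/C. At the smallest sizes Group B still needs 35 + 50 = 85. At 300 an even split would be 100 per group, but Group A is 50.

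**5. Illustration of the loss.** Assume that the even split is followed strictly and that Group B's 67 places hold only these two diagnoses. Power for idiopathic VF is 1 − 0.96^n.

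| Concealed Brugada | McNemar power, exact / asymptotic | Idiopathic VF | Power for at least one case |
|---|---|---|---|
| 50 | 97.7% / 97.9% | 17 | 50.0% |
| 35 | 89.2% / 90.7% | 32 | 72.9% |
| 33 | 86.8% / 88.8% | 34 | 75.0% |
| 17 | 46.8% / 58.9% | 50 | 87.0% |

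No row reaches both 90% and 87%. The manifest Brugada comparison is not harmed, because 50 fit within 67 in both Group A and Group C.

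**The case against.** The best defence is that 200 is the Study B total. The four powered cohorts sum to exactly 200. The other 100 come in a separate paragraph tied only to UHF-ECG, and the Study C procedure is a recording of up to 5 minutes followed by event follow-up, with no prolonged wear. Section 6 counts patients who have completed the 3-month interval, which is the Study B procedure. On that reading the section 6 count could stand. This is plausible but not stated: section 3.3 gives Study B all of Groups A-C, and section 6 speaks of the prospective studies together. It also leaves section 3.1 wrong, since that section gives 200 as the total for the prospective studies.

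Three further points have some force:

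- The even split is an approximate aim and not a quota, so the most lopsided rows in the illustration should carry little weight. Even so, the aim cannot reasonably cover a Group B twice the size of each other group.
- The UHF-ECG risk analysis would not be empty without the 100, because Study C also draws on the Brugada and idiopathic VF patients. It would lose the cohort that section 7 sets aside for the high-risk and low-risk comparison.
- That cohort is pilot work with no power claim, and the powered comparisons fit within 200. This limits the damage but does not make the two totals agree.

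**Conclusion.** The concern holds and must be fixed. Section 7 plans 300 participants, 1.5 times the 200 in sections 3.1 and 6; without volunteers the figure is 250. Within 200 there are between 0 and 25 places for the 100 other patients, depending on whether the powered cohorts are filled as planned or cut to their smallest stated sizes. The even split fails at 200 and at 300. These results are sums of the protocol's own figures and need no outside assumption.

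The power losses do rest on assumptions: a strict even split and a Group B made up of two diagnoses only. If 50/50/50/50 is recruited, every stated power holds and the cost falls wholly on the other-conditions cohort.

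**What to change.** Put one recruitment table by diagnosis in the protocol and make sections 3.1, 6 and 7 agree with it. Replace the even-split sentence with those quotas, and tie the section 6 end rule to them. The sponsor then chooses one option:

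1. **Keep 200 as 50/50/50/50.** Withdraw the 100-patient cohort and state that the UHF-ECG risk analysis rests on the four remaining cohorts. Cost: wording only, but that cohort is lost.
2. **Keep 200 with smaller powered cohorts and a stated number of other patients.** Restate each power at its quota. Cost: no extra patients, but lower stated powers or no allowance for loss, and at most 25 other patients if the smallest sizes are kept.
3. **Recruit 300.** Correct the total in section 3.1 and the count in section 6. Cost: 100 more patients, who under section 3.3 would also have ambulatory monitoring. If they are meant for Study C only, say so in sections 3.1 and 3.3, and state in section 6 that the count of 200 refers to Study B.
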